## **5.3. Treatment Assignment Procedures**

### **5.3.1. Randomization Procedures**

This is an unblinded, individually randomized study. Enrolled children will be randomized in a 1:1 ratio to one of two arms:

- Group 1: 314 children receiving one dose of CD-JEV vaccine and one dose of MMR vaccine concurrently at enrollment;
- Group 2: 314 children receiving one dose of MMR vaccine at enrollment and one dose of CD-JEV 56 days later.

A detailed randomization standard operating procedure (SOP) will be developed and executed prior to study initiation to generate the allocation sequence. The study will use a random permuted block design to assure as close to 1:1 group balance is maintained.

PATH will maintain all electronic documents generated as part of the randomization in a secure location not accessible to other study staff involved in the trial.

### **5.3.2. Allocation and Masking Procedures**

A detailed allocation SOP will be developed in cooperation with the investigator. This allocation SOP will specify how enrolled participants must be allocated to study Group 1 (CD-JEV and MMR concurrently) or Group 2 (MMR alone and CD-JEV 56 days later).

Commercial presentations of MMR and CD-JEV will be used in this study. MMR will be procured from the Philippine distributor for MMR vaccine and CD-JEV will be donated by CDIBP. Since this is an open-label trial with licensed vaccines, parents of participants will know whether their child is in the experimental group receiving MMR and CD-JEV concurrently. While study vaccines will not be masked, they will be labeled for clinical trial use per section 6.1.4.

Laboratory staff performing serologic tests will remain masked to individual group assignments during the study period until database lock is performed. Study statisticians will be unmasked to study group identification for the purposes of performing statistical analyses.

### **5.3.3. Adherence to Randomization**

The investigator or designee will document adherence to the allocation SOP. Additionally, specific study vaccines given to each individual participant will be documented.

### **5.3.4. Reasons for Withdrawal**

After enrollment, a participant might be withdrawn from participation for several reasons:

- The investigator requests withdrawal of the participant because the child is not eligible or is no longer eligible, because he/she has developed an AE requiring withdrawal, or because the participant is non-compliant;
- A participant voluntarily withdraws at his/her own request;
- A participant is lost to follow-up;
- The trial is terminated prematurely by the sponsor, institutional or ethical review committees, or the regulatory agency; or
- Death of the participant.

### **5.3.5. Handling of Withdrawals**

In case of premature withdrawal for any reason, the investigator should exert her best effort to:

- Conduct an interview to determine if the participant has had any reaction or AE (serious or non-serious) that has led to the withdrawal during the 28-day period after any study vaccination. Where possible, the investigator should visibly or physically assess any reported adverse reaction or AE.
- Attempt to complete all scheduled procedures and evaluations planned for the next study visit.
- Document the reason for premature withdrawal.
- Complete the end of the study record.

Withdrawal of a participant by the investigator may occur only if the child is identified to have one of the listed exclusion criteria or if continued participation threatens the child's well-being or the integrity of the

study. If the participant develops a reaction to study vaccine which the investigator believes threatens the child's well-being, the withdrawn participant must be treated or transferred to a treatment facility.

If premature withdrawal is initiated by the parent or investigator, PATH must be informed within 48 hours about all instances (excluding lost to follow-up).

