### 5.2. Participant Exclusion Criteria

No participant receiving study vaccines may have any of the following exclusion criteria at study entry:

- Previous receipt of any measles-mumps-rubella containing vaccine.
- Previous receipt of any Japanese encephalitis vaccine.
- History of measles, mumps, rubella, or Japanese encephalitis infection.
- Administration of any other vaccine within 28 days prior to administration of a study vaccine or planned vaccination of any vaccine other than catch-up doses of routine EPI vaccines or oral polio vaccine during the 28 days after study vaccination.
- History of allergic disease or known hypersensitivity to any component of the study vaccines and/or following administration of vaccines included in the local program of immunization.
- Use of any investigational or non-registered drug within 90 days prior to the administration of

study vaccines or planned administration during the study period.

- Administration of immunoglobulins and/or any blood products within 90 days prior to the administration of study vaccines or planned administration during the study period.
- Chronic administration (defined as >7 days) of immunosuppressing or other immune-modifying agents for 14 days before or after vaccination (including systemic corticosteroids equivalent to prednisone  $\geq 0.5$  mg/kg/day; topical and inhaled steroids are allowed).
- Primary or acquired immunodeficiency, including HIV infection, or a family history of congenital or hereditary immunodeficiency as reported by parent.
- Acute or chronic, clinically significant pulmonary, cardiovascular, hepatic, or renal functional abnormality, as determined by medical history or physical examination, which in the opinion of the study physician, might interfere with the study objectives.
- Severely malnourished infants as measured by the World Health Organization weight-for-height tables (Z-score < -3).
- Any condition or criterion that, in the opinion of the study physician, might compromise the well-being of the participant, compliance with study procedures, or interpretation of the outcomes of the study.
- Acute illness at the time of enrollment defined as the presence of a moderate or severe illness with fever (axillary temperature  $\geq 38.0^{\circ}\text{C}$ ) or without fever (severity determined at the discretion of the study physician).

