### **6.4. Concomitant Medications/Treatments**

All medications administered must be checked against the inclusion/exclusion criteria. All medications used between enrollment and 28 days post-vaccination, except for topical treatment or vitamins, will be reported, including the following details: international non-proprietary name, dose, frequency, route, duration (start and end date), and indication for the treatment. The parents will be requested not to give the child preemptive analgesic or antipyretic drugs, as they may change the reactogenicity profile of the vaccine.

Injection of immunoglobulin, use of a systemic corticosteroid therapy for more than one week (inhalation will not be considered as systemic treatment) within 14 days before or after vaccination, or administration of any other immunomodulating agent, except the vaccines anticipated in the protocol, during the study period will lead to exclusion of the participant from the per-protocol statistical analysis.

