### 7.14. Allowable Schedule of Study Visits

For clarity, per-protocol timing of key study visits is provided below. No child should be dropped from the study solely on the basis of a visit falling outside of an allowable time-frame for that visit if there is good faith attempt by study staff and the participant's parent(s)/guardian(s) to adhere to the protocol.

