## **15.6. Protocol Deviations**

A protocol deviation is any noncompliance with the clinical study protocol, GCP, or the site manual of procedures. The noncompliance may be either on the part of the participant, the investigator, or the study site staff. As a result of any deviations, corrective actions are to be developed by the site and implemented promptly. Examples of protocol deviations include the following:

- Non-adherence to inclusion and/or exclusion criteria.
- Irregular or improper implementation of the trial product.
- Unnecessary repeated performance of any planned procedures or tests.
- Changing the interval between two visits or procedures more than allowed by the protocol.
- Incorrect or careless documentation of study procedures on primary documents or required logs.
- Premature withdrawal of a participant for any reason, even if withdrawal is in the best interest of the well-being of the participant.

Trial procedures shall not be changed without the consent of PATH. Insignificant violations of the protocol will be examined on an individual basis taking into account information documenting the reason(s) that the deviation occurred.

It is the responsibility of the site to use continuous vigilance to identify and report deviations to PATH in a timely manner after identification. Reports of protocol deviations must be sent to WIRB and the RITM IRB, as required per their respective guidelines. The investigator and study staff are responsible for knowing and adhering to IRB and IEC requirements. PATH will assist the investigator in all reporting to WIRB or file reports on behalf of the investigator.

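### An infant whom the investigator withdraws after dosing leaves active SAE follow-up at the next visit, although SAEs to Day 112 are a stated outcome

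*Protocol*

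**What the plan says.** Protocol 5.3.4 lists reasons for withdrawal from participation. The investigator may request it "because the child is not eligible or is no longer eligible, because he/she has developed an AE requiring withdrawal", or for non-compliance. Protocol 5.3.5 narrows this: "Withdrawal of a participant by the investigator may occur only if the child is identified to have one of the listed exclusion criteria", or if staying in threatens the child's well-being or the integrity of the study.

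For any premature withdrawal, 5.3.5 asks for four best-effort steps:
- an interview about "any reaction or AE (serious or non-serious) that has led to the withdrawal during the 28-day period after any study vaccination";
- "Attempt to complete all scheduled procedures and evaluations planned for the next study visit";
- a record of the reason;
- completion of the end-of-study record.

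Neither document tells sites that an infant who should receive no further study vaccine can remain in scheduled follow-up. The nearest retention rule is Protocol 7.14, which covers visit timing only: "No child should be dropped from the study solely on the basis of a visit falling outside of an allowable time-frame".

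On the outcome side, Protocol 3.2.2 makes SAEs over the whole study a secondary outcome. SAP 7.2 reports the number and proportion of infants with at least one SAE per group, with an exact 95% CI. The denominator is the ITT set, or the safety set when applicable. Protocol 11.2.1 keeps withdrawn infants in the ITT set up to the time of withdrawal.

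**The concern.** The plan states a handling rule that shortens follow-up for an outcome defined over the full study. An infant withdrawn early remains in the SAE denominator, and SAP 7.2 has no person-time or censoring method. The unobserved days therefore count as free of SAEs.

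The infants concerned are not a random sample. They are children with an adverse event judged to require withdrawal, or with a condition such as immunodeficiency found after a live vaccine was given. Protocol 2.1.6 itself names a theoretical risk if the JE vaccine strain replicates unchecked. New SAEs in these children are ones the safety profile should capture.

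A lesser loss is the Day 56 serum. An infant withdrawn before the Day 28 visit has no MMR serum scheduled at the next visit, so cannot contribute an MMR result to the supportive ITT immunogenicity analysis.

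**Working it through.** **1. What the next visit covers** (Protocol 7.4 to 7.7 and 7.14). Before the Day 28 visit, the next contact is Day 2, 14 or 28. None draws MMR serum: Group 1's Day 28 blood is for anti-JE and Group 2 has no blood then. Both groups give MMR serum at Day 56. After the Day 28 visit and before Day 56, the next visit is Day 56, so MMR serum would be attempted.

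**2. Days without active SAE enquiry** = 112 − day of next visit.

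| Next visit | SAE days uncovered | Unsolicited-AE days uncovered after the first vaccination (of 28) |
|---|---|---|
| Day 2 | 112 − 2 = 110 (98.2%) | 28 − 2 = 26 |
| Day 14 | 112 − 14 = 98 (87.5%) | 28 − 14 = 14 |
| Day 28 | 112 − 28 = 84 (75.0%) | 0 |
| Day 56 | 112 − 56 = 56 (50.0%) | 0 |

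**3. Illustrative size.** The documents give neither a withdrawal rate nor an SAE risk. Assume that 1 to 3% per group (3 to 9 of 314) are withdrawn before Day 28, and that the 112-day SAE risk is 2 to 10%, spread evenly over time.
- Follow-up planned per group: 314 × 112 = 35,168 infant-days.
- Follow-up lost: 3 × 84 = 252 days (0.7%) to 9 × 110 = 990 days (2.8%).
- Expected missed SAEs per group: 3 × 0.02 × 84/112 = 0.045 to 9 × 0.10 × 110/112 = 0.88.
- Effect of one missed SAE: 1/314 = 0.32 percentage points. The Clopper-Pearson 95% interval is 0 to 1.17% for 0/314 and 0.01 to 1.76% for 1/314.

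The upper end needs all nine infants to be withdrawn before the Day 2 call.

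**4. Supportive ITT seropositivity.** Assume equal true rates p in the two groups (90% rubella, 95% measles, from Protocol 11.4), 9 lost in one group and 3 in the other, and lost infants seropositive at rate q. The observed rate with k lost is (314p − kq)/(314 − k).
- Rubella, q = 70%: 90.59% against 90.19%, a difference of 0.40 points. Measles with q = 75% also gives 0.40.
- Extreme case, q = 0: 1.79 points (rubella) and 1.89 points (measles).
- Equal losses, or lost infants who respond like the rest: zero. Reversing the imbalance reverses the sign.

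The margin is 10 points.

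**5. Power, starting from the plan's own figure.** The Farrington-Manning formula is n = [(1.960 s₀ + 1.645 s₁)/0.10]². For rubella at 90% in both groups, s₁ = √(2 × 0.9 × 0.1) = 0.424. The restricted rates under the null are 83.1% and 93.1%, so s₀ = 0.452. This gives n = 250.7, rounded up to 251 evaluable per group, and 251/0.80 = 313.75, or 314. The plan's figure is reproduced. At 251 per group, power is 95.0% for rubella and 99.7% for measles, with product 94.7%.

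The infants at issue fail either the eligibility condition or the condition of having received all assigned vaccines (Protocol 11.2.3.1 and 11.2.3.3). They are outside the per-protocol sets whether or not they stay in follow-up, so these figures do not move.

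**The case against.** The case against is substantial, and much of it stands.

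- **The protocol already leans towards retention.** Withdrawal is permissive, 5.3.5 restricts when the investigator may use it, and 15.6 counts as a deviation "Premature withdrawal of a participant for any reason, even if withdrawal is in the best interest of the well-being of the participant". A reader might infer that the protocol requires these infants to leave, or forbids withholding a dose while follow-up continues. It does neither. It offers no stated alternative to withdrawal, and it limits best effort once withdrawal happens.
- **Few infants will be affected.** After Day 0 no dose is due until Day 56 (Group 2) or Day 84 (Group 1), so a decision to stop vaccine rarely arises before Day 28. The clearer route is an exclusion criterion found after dosing.
- **Some events are still captured.** The Day 2, 14 and 28 contacts ask about any reaction, SAE or care sought (7.4 to 7.6), so the narrow exit interview is not the only enquiry. The identification card and the instructions to parents give a passive route (7.3). Known events are followed (9.2.3, 9.2.4, 9.4). None of this is active enquiry for new SAEs up to Day 112.
- **Much early loss cannot be recovered.** Parents who withdraw consent and families lost to follow-up are beyond this fix. The 1 to 3% in the illustration is therefore generous if it is read as all withdrawals.
- **The shortfall is partly visible.** Withdrawals and reasons are tabulated by group (SAP 4.3), and the SAE proportion is descriptive.

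A reader might also see a contradiction over steroids. Section 5.2 lists prolonged use of "immunosuppressing or other immune-modifying agents for 14 days before or after vaccination", which could be met after dosing and so permit withdrawal, whereas under 6.4 such treatment "during the study period will lead to exclusion of the participant from the per-protocol statistical analysis". The documents do not support a conflict. The 5.2 criteria apply at study entry, 6.4 is the specific rule for later treatment, and 5.3.5 says may, not must. Section 6.4 is better read as the model for the fix.

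**Conclusion.** The concern holds as a minor design point. The withdrawal rule ends active SAE enquiry at the next visit for infants whom the investigator withdraws after dosing. If that happens before the Day 28 visit, 75 to 98% of the 112-day period is uncovered. This follows from the schedule alone and needs no assumption beyond the next visit taking place.

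The effect on the trial's results is small. Fewer than one missed SAE per group is expected, and the supportive ITT difference moves by about 0.4 points, or at most 1.9 in the extreme case. Both results rest on assumed rates that the documents do not give, and the recoverable share is probably smaller.

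A reader might infer from the missing Day 56 serum that the non-inferiority conclusion or its power is at risk. The documents do not support that. The infants are excluded from the per-protocol sets either way, and the 20% non-evaluable allowance already includes loss to follow-up. The reason to act is complete safety capture in infants given live vaccines, at little cost.

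**What to change.** In Protocol 5.3.4 and 5.3.5, separate stopping study vaccine from withdrawing from the study. State that an adverse event, or an exclusion criterion found after dosing, leads to no further study vaccine where needed and to per-protocol exclusion where applicable, as 6.4 already does for restricted treatments, but not to withdrawal from follow-up. Unless the parent withdraws consent or the visits themselves threaten the child's well-being, keep:
- the scheduled safety visits and SAE enquiry to Day 112;
- the scheduled bloods, above all Day 56, for the supportive ITT analysis.

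In SAP 4.3, report the two statuses on separate rows by group. The per-protocol definitions and the sample size do not change.

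The cost is low. A protocol amendment needs ethics approval (Protocol 14.2 and 14.3), and the wording must agree with the consent form, which was not available here. The visits are already planned. A few families would continue them without further vaccine and give the 3 to 5 mL Day 56 sample; in Group 1 the Day 28 sample would also be taken if still due.

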### **5.3.6. Suspension or Termination of Study**

The trial might be suspended at any time by PATH or by any ethical review committee overseeing this study for any safety concern. This includes, for example, and without limitation, an SAE resulting in death that is viewed to be related to receipt of study vaccine or an unusually high rate of SAEs. PATH may suspend the study in the event that study conduct is found to be below Good Clinical Practice (GCP) standards.

In the event of the appearance of new data that indicate an increased level of risk to study participants, the clinical trial will be suspended until PATH and all ethical review committees have reviewed relevant data and agreed that the trial may proceed.

## **6. STUDY VACCINES**

### **6.1. Study Vaccine Descriptions**

#### **6.1.1. Live, Attenuated SA 14-14-2 JE Vaccine**

The derivation of the live, attenuated Japanese encephalitis virus strain, SA 14-14-2, was through an empirical process of serial passage, principally in PHK cells. The live, attenuated SA 14-14-2 JE virus genome has 57 nucleotide changes from that of wild-type JE virus, resulting in 24 amino acid changes. Eight amino acid changes in the E protein gene, which is strongly associated with neurovirulence, result in attenuation. These eight critical amino acid changes have been shown to be genetically quite stable.

The WHO prequalified live, attenuated SA 14-14-2 JE vaccine manufactured by CDIBP and marketed as CD-JEVAX™ or RS.JEV™ is a preparation of live, attenuated JE virus (strain SA 14-14-2) grown in culture on a monolayer of PHK cells. After cultivation and harvest, an appropriate stabilizer is added in the virus suspension, which is then lyophilized. Live, attenuated JE virus (strain SA 14-14-2), minimum essential medium, and human serum albumin are the major components of the final vaccine.

#### **6.1.2. Measles, Mumps, Rubella Vaccine**

The MMR vaccine manufactured by GlaxoSmithKline, Inc., and licensed as Priorix® in the Philippines is a lyophilized vaccine containing live, attenuated Schwarz measles virus produced in chick embryo cells, RIT 4385 mumps (derived from Jeryl Lynn strain) produced in chick embryo cells, and Wistar RA 27/3 rubella virus propagated on human diploid cells. Each single human dose when reconstituted in a volume of 0.5 mL contains not less than 1000 CCID50 of measles virus, 5012 CCID50 of mumps virus, and 1000 CCID50 of rubella virus. The vaccine meets the requirements of WHO Technical Report Series 840 (1994).

### **6.1.3. Acquisition**

RITM will be responsible for vaccine receipt and management of the vaccine. Appropriate vaccine acquisition and handling SOPs will be developed in collaboration with the investigator. Extra doses of both vaccines will be provided and shall be used when the initially allocated dose is broken, damaged, or unusable. For CD-JEV, the manufacturer will donate these vaccines free of charge; whereas, MMR vaccine will be procured. Vaccine accountability practices will be established to ensure receipt, storage, administration, and disposal are documented and monitored. The investigator and their institution will receive no monetary compensation from the manufacturers for their participation in this study.

### **6.1.4. Packaging and Labeling**

Both study vaccines will be provided in their commercial presentation, containing their package insert. The commercial vial labels for these vaccines should remain intact. Study products will be labeled in compliance with any applicable national regulations. At a minimum, an additional label will be affixed to each box and will bear the following information:

- Study number
- Legal information: "For Clinical Trial Use Only"

### **6.1.5. Product Storage and Stability**

CD-JEV and MMR vaccine should be stored in a refrigerator or cold box at a temperature ranging from +2°C to +8°C and protected from light. Storage temperature should be monitored and documented on an appropriate form during the entire trial.

The vaccines should never be frozen. In case of deep freezing or accidental disruption of the cold chain, the vaccine should not be administered and the investigator or the responsible person should contact PATH to receive further instructions.

## **6.2. Dosage, Preparation, and Administration of Study Vaccines**

The vaccines in general should be gently shaken prior to administration to assure homogenous suspension. CD-JEV will be administered subcutaneously into the anterolateral aspect of the right upper thigh. MMR vaccine will be administered subcutaneously into the anterolateral aspect of the left upper thigh.

CD-JEV will be supplied in 5-dose vials as a lyophilized powder that looks like a milky-white crisp cake. After reconstitution, it turns into a transparent orange-red liquid. Each 0.5 mL human dose for subcutaneous injection contains not less than 5.4 log PFU of live JE virus. A single dose of 0.5 mL should be administered by subcutaneous injection with the rest of the vial contents discarded.

Measles-mumps-rubella vaccine appears as a white to slightly pink dry cake. It will be supplied in its monodose commercial presentation. The vaccine should be reconstituted only with the diluent supplied (sterile water for injection). A single dose of 0.5 mL should be administered by subcutaneous injection.

Standard immunization practices will be observed and care will be taken to administer the injections. As with all injectable vaccines, appropriate medical treatment, staff, and supervision will be readily available in case of rare anaphylactic reactions following administration of the study vaccine and epinephrine 1:1000 will be available in case of any anaphylactic reactions.

